7.2 Analysis Populations

The population for all analyses will be the safety population, defined as all patients who had the IDDD implant or received at least one dose of study drug in the extension study (SHP-610-201). Safety analyses will be conducted according to the treatment received. Device related analyses will be conducted in the subset of patients in the safety population who had the device implanted.

7.3 Subject Disposition

The number of patients signed informed consent; the number and proportion of patients randomized, included in the safety population, completed the study, discontinued prematurely, completed the treatment period, and still in study will be presented in a summary table by treatment group; reasons for discontinuation/withdrawal will also be summarized. Subject disposition will also be presented in a listing.

7.4 Demographics and Baseline Characteristics

Demographic data and baseline characteristics will be summarized by the individual treatment group and the overall HGT-1410 treatment group for the safety population. Demographic data and baseline characteristics will be also presented in a listing.

7.5 Protocol Deviations

Reported protocol deviations and patient data will be examined prior to database lock to determine if conditions set forth in the study protocol have been violated. Protocol violations will be defined as any major protocol deviation that affects study evaluations, such as a significant violation of admission (inclusion/exclusion) criteria. The protocol deviations will be presented in a listing and all protocol violations will be indicated by a flag.

7.6 Medical History

Medical history will be coded using Medical Dictionary for Regulatory activities (MedDRA) Version 17.1 and provided as a listing.

7.7 Treatment Compliance and Extent of Exposure

The total number of doses of study drug, the number of doses received via IDDD, the number of doses received via LP, the average duration of IT administration and treatment compliance will be summarized by treatment group for the safety population.

Duration of IT administration, summarized in weeks, is calculated by subtracting the date of first dose from date of last dose.

Duration of each IT administration (in minutes) is calculated by subtracting the IT administration start time from the IT administration end time.

Treatment compliance is defined as: $[(\text{Number of Complete IT administrations}) \div (\text{Expected Number of IT administrations})] * 100$.

The IT administration of study drug will be also presented in a listing.

7.8 Analysis of Efficacy

7.8.1 Primary Analysis

The primary objective of this study is to evaluate long-term safety of HGT-1410 in patients with MPS-III. Therefore, the primary analysis will be discussed in the safety analysis section, Section 7.10.

7.8.2 Secondary Efficacy Analysis

7.8.2.1 Bayley Scales of Infant Development, Third Edition (BSID-III)/

The BSID-III data including developmental quotient (DQ), age equivalent scores, growth scores, total raw scores and scaled scores for each subtest (Cognitive, Receptive Communication, Expressive Communication, Fine Motor, and Gross Motor) will be presented in a listing only.

The KABC-II is an alternative to BSID-III. Few subjects were administered KABC-II scale; however, these scores were considered invalid by the sites, hence no data for KABC-II will be presented.

7.8.2.2 Vineland Adaptive Behavior Scales, Second Edition (VABS-II)

The VABS-II data including age equivalent scores, DQ, raw scores, and standard scores for each domain will be presented in a listing only.

7.8.2.3 Brain MRI

Although several MRI parameters will be captured, only the grey matter volume, the white matter volume, and the total intracranial CSF volume will be presented in a listing.

7.9 Analysis of Pharmacokinetic and Pharmacodynamic Data

7.9.1 Pharmacokinetic Measurement and Parameters

As the treatment period of the study was closed earlier than planned, there were few PK samples collected and hence no analysis on pharmacokinetic measurement and parameters will be provided.

7.9.2 Pharmacodynamic Analyses

The levels of GAG (heparin sulfate) in CSF and urine (glycosaminoglycans/creatinine) are pharmacodynamic endpoints. The data for pharmacodynamic endpoints will be presented in a listing only, with the MRI data.

7.10 Analysis of Safety

7.10.1 Adverse Events

Once the patient has signed the informed consent form, AEs will be recorded throughout the study and at early termination. AEs will be coded using Medical Dictionary for Regulatory Affairs (MedDRA) version 17.1.

Treatment-emergent AEs, defined as all AEs from the time of initial IDDD implantation (or first dose if earlier) in either HGT-SAN-093 or SHP-610-201 to the data cut-off date, or 30 days after the date of last dose or 2 weeks after the date of device explant (whichever is later) if early termination, will be summarized. For each treatment group, the number and percentage of patients having an AE and the number of events, by system organ class (SOC) and preferred

term will be presented. Treatment-emergent AEs will also be summarized by severity and degree of relationship to study drug. In the case of multiple occurrences of the same AE (at the preferred term level) in an individual patient, the AE that is classified as the most severe (ie, maximum severity) will be identified for the analysis by severity and the AE that has the closest relationship to study drug/procedure will be identified for the analysis by relationship. In general, an AE will be considered a treatment-emergent AE if it cannot be definitively categorized otherwise by documentation that its onset preceded either IDDD surgery or first dose.

Serious adverse events will be similarly summarized by SOC and preferred term.

All treatment-emergent AEs, serious or life-threatening treatment-emergent AEs, treatment-emergent AEs leading to permanent discontinuation of study drug or resulting in death will be presented in a separate listing, respectively.

7.10.1.1 Investigational Product-Related AEs

Treatment-emergent AEs deemed by the investigator to be related (probably, possibly, or definitely related) to the investigational product (HGT-1410) will be summarized by presenting the number and percentage of patients having an AE and the number of events, by SOC and preferred term.

7.10.1.2 IDDD and Surgical Procedure-Related AEs

Intrathecal drug delivery devices and procedure-related AEs will be summarized within SOC by preferred term. Separate tabulations will be provided for AEs related to the IDDD, device surgical procedure, and IT administration process.

Intrathecal drug delivery device and procedure related events will be analyzed in the subset of patients in the safety population who underwent surgery for IDDD implantation.

7.10.2 Clinical Laboratory Evaluation

The measurements of each laboratory parameter (serum chemistry, hematology, urinalysis and CSF) and the corresponding normal ranges will be converted to Standard International (SI) units, if needed.

Each laboratory result will be categorized as a patient having had (1) an abnormal and clinically significant (CS) value at any time between baseline and the data cut-off date, (2) no CS values at any time between baseline and the data cut-off date, but had at least 1 abnormal and not CS (NCS) value, and (3) no CS or NCS values at any time between baseline and the data cut-off date. For any patient who experiences a CS laboratory result at any time between baseline and the data cut-off date that was not CS at baseline (or the most recent non-missing value prior to the start of the treatment), their entire profile for that particular laboratory parameter will be presented as a listing.

If more than one laboratory result is reported per assessment time per parameter, the last non-missing result will be selected for analysis.

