2. INTRODUCTION

2.1 Purpose of the Statistical Analysis Plan

This statistical analysis plan (SAP) provides a technical and detailed elaboration of the planned interim analyses for protocol SHP-610-201 amendment 2, a Phase IIb, open-label extension of study HGT-SAN-093 evaluating the safety and efficacy of HGT-1410 (Recombinant Human Heparan N Sulfatase) administration via an intrathecal drug delivery device in pediatric patients with mucopolysaccharidosis type IIIA disease. Shire made a decision in August 2016 to terminate the Sanfilippo Syndrome Type A development program, including this extension study, due to the failure to meet the prespecified efficacy criteria in the pivotal Phase 2 study, HGT-SAN-093, and the resulting inability for the study to yield clinical proof-of-concept. After notification of early study termination, several investigators informed Shire that the IDDDs would remain implanted since in their opinion removal of devices would result in an increased risk to the patients. Therefore, this extension study (SHP-610-201) remains ongoing and has been extended to allow for safety follow-up of patients with partial or full devices still implanted after completion of the treatment period of the study. The statistical analyses and summary tabulations described in this interim SAP will provide the basis for the results sections of the abbreviated clinical study report (aCSR). An aCSR will be written to describe the results of the treatment period of the study, as the study is not intended to contribute to the evaluation of product effectiveness or to provide definitive information on clinical pharmacology. Full safety information will be reported.

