5. EFFICACY AND SAFETY ENDPOINTS

5.1 Primary Endpoint

Safety is the primary objective of the study and will be assessed during the study by the following:

- Collection of adverse events (AEs; by type, severity, and relationship to treatment [HGT-1410, the IDDD, device surgical procedure, or IT administration process])
- Changes in clinical laboratory testing (serum chemistry, hematology, urinalysis)
- Physical examination
- Vital signs
- Twelve-lead electrocardiogram (ECG) recordings
- CSF laboratory parameters (including chemistries, cell counts)
- Anti-rhHNS antibodies in CSF and serum, including determination of antibodies having enzyme neutralizing activity

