7. STATISTICAL ANALYSIS

7.1 General Methodology

Statistical analysis will generally be performed by the Biometrics Department of Shire using SAS statistical software (SAS Institute, Cary, NC, USA). Analysis of any PK and health economics and outcomes data will be performed by the Shire Clinical Pharmacology and Pharmacokinetics group and the Health Economics and Outcomes Research groups, respectively. The analysis methods for all other study data (demographic and baseline characteristics, efficacy variables, and safety variables) will be detailed in this SAP.

Summary statistics for continuous variables will include the n, mean, standard deviation, median, minimum, and maximum. Categorical variables will be summarized in a contingency table by the frequency and percentage of patients in each category.

Unless otherwise indicated, all summary statistics will be presented by treatment groups (either Q2W or Q4W) to which the patients were randomly assigned (for patients who were initially assigned to Q2W or Q4W group in Study HGT-SAN-093 or patients who were assigned to no-treatment in HGT-SAN-093 and were randomly assigned to Q2W or Q4W in Study SHP-601-201).

No summary statistics and hypothesis testing will be presented for efficacy data. Instead, subject listings will be presented for the selected efficacy endpoints.

Data from Study HGT-SAN-093 will be combined with that of Study SHP-610-201 for analysis, for subjects who enrolled in SHP-610-201. The data included for treated patients in HGT-SAN-093 starts from the baseline of Study HGT-SAN-093 and for patients who received no treatment in HGT-SAN-093 from the baseline of Study SHP-610-201. Baseline is the assessment obtained prior to the first dose of HGT-1410.

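### Laboratory changes are part of the primary safety assessment, but 7.10.2 describes no change from baseline, no classes set against baseline and no full listing of laboratory or CSF values

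*SAP*

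**What the plan says.** Section 5.1 opens with "Safety is the primary objective of the study and will be assessed during the study by the following" and gives seven components. One is "Changes in clinical laboratory testing (serum chemistry, hematology, urinalysis"). A separate one is "CSF laboratory parameters (including chemistries, cell counts"), which is not worded as a change. Section 2.1 of the interim SAP says "Full safety information will be reported". Section 2.1 of the SAP that precedes it in the file goes further and commits the report to the same safety content as a full report.

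Section 7.10.2 of the interim SAP sets three classes:

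- Class 1: "Each laboratory result will be categorized as a patient having had (1) an abnormal and clinically significant (CS) value" at any time from baseline to the cut-off.
- Class 2: no CS value, "but had at least 1 abnormal and not CS (NCS) value".
- Class 3: "3) no CS or NCS values at any time between baseline and the data cut-off date".

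Actual values are listed only where a patient has a CS result that was not CS at baseline, and then only for that parameter. Section 7.10.2 of the preceding SAP is nearly the same.

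Section 7.1 gives the default for numeric data: "Summary statistics for continuous variables will include the n, mean, standard deviation, median, minimum, and maximum". Section 8.1 then restricts summary statistics to baseline characteristics, exposure and adverse events. It names two kinds of data as not analysed, ITQoL and pharmacokinetics. Laboratory data are not among them.

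**The concern.** A component of the primary assessment is worded as change, yet its analysis section computes no change. The classes describe only what happened after baseline. A child who was abnormal throughout and a child who became abnormal on treatment can both fall in class 2.

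The stated reason for abbreviating the report is that the study is not meant to support effectiveness or clinical pharmacology. That is not a reason to thin out safety data. Yet BSID-III, VABS-II, MRI volumes, GAG levels, vital signs around dosing and antibody status are all to be listed, while numeric laboratory and CSF results are listed only on a CS trigger.

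In an uncontrolled study of at most 21 children, within-patient movement over time is the main laboratory information available. If the plan is followed as written, a reader of the report could not tell whether values drifted, in which direction, or by how much, unless a child reached a new CS result.

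**Working it through.** The plan has no figure to reproduce: section 4.5 makes no sample size calculation and gives only the expected maximum of 21. The check is mainly one of reading, followed by an illustration.

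**Step 1. What each described output shows about laboratory values (interim SAP).**

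| Type of shift | Three classes (7.10.2) | Value listing (7.10.2) |
|---|---|---|
| Within the normal range | No trace: class 3 before and after | Not triggered |
| Past the normal limit, below CS | Class 2 rises, but with no baseline class to compare and no size or direction | Not triggered |
| To a new CS value | Class 1 rises | That patient's profile, that parameter only |

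Section 7.10.2 does not say that the classes are tabulated, and 8.1 appears to exclude a summary of them. The addendum (6.5.2) plans a by-subject laboratory listing, but only for tests prompted by a device-related AE in the safety follow-up period. It does not cover the treatment period.

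**Step 2. How class 2 behaves.** Assumptions, none from the SAP: one parameter in baseline SD units, normal range ±1.96 SD, CS beyond 4 SD, 21 children, five post-baseline tests, within-patient correlation 0.5. Expected class 2 count = 21 × simulated class share:

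- no shift: 21 × 0.186 = 3.9
- 0.5 SD shift: 21 × 0.254 = 5.3
- 1 SD shift: 21 × 0.433 = 9.1

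Class 2 does respond to a shift that crosses the limit. But about four children are expected there with no shift at all. With 20 tests and no shift the figure is 21 × 0.417 = 8.8. Without a baseline tabulation the count cannot be interpreted as change.

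**Step 3. Chance that no child's values are listed for a parameter.** Let p be the probability that a child is not CS at baseline and has at least one later CS value. Then P(no listing) = (1 − p)^21. The assumed shift is 0.75 SD, with correlation 0.5 to 0.7 and p by simulation.

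| Post-baseline samples | CS beyond 3 SD | CS beyond 4 SD |
|---|---|---|
| 1 | 78% | 99% |
| 5 | 36–44% | 94–95% |
| 20 | 6–16% | 83–88% |

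For example, with CS at 3 SD, five samples and correlation 0.5, p = 0.0475 and (1 − 0.0475)^21 = 0.36. The range is about 6% to 99%. It is driven by two inputs that the SAP does not give: how many samples each child has, and where CS lies.

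**Step 4. What a change summary could show.** SD of change = √(2(1 − correlation)), and the 95% half-width for the mean change = 2.086 × SD of change ÷ √21. Correlation 0.5 gives 2.086 × 1.00 ÷ 4.583 = 0.46 SD. Correlation 0.8 gives 2.086 × 0.63 ÷ 4.583 = 0.29 SD. Even in 21 children, a descriptive table would be informative.

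**The case against.** The strongest reply is that the reduction is deliberate and disclosed. The programme was terminated, the report is abbreviated, and 8.1 openly restricts summary statistics. A promise of full safety information does not by itself prescribe tables of mean change, and in at most 21 children a full listing might serve as well. Much of this stands: the choice is not hidden, and by-visit means are not the only remedy. But a limit on summary statistics does not explain the absence of a full listing, and 8.1 does not name laboratory data among what is left out.

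A reader might infer more than the text supports:

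- **That the primary endpoint as a whole goes unanalysed.** It has seven components. Laboratory change is one, and the CSF component is not worded as change.
- **That a shift below the CS level appears in no output.** Class 2 is the class for abnormal values below CS and would rise if values left the normal range. The TFL shells, which hold the output list, are also not at hand.
- **That the classes rest on an unblinded investigator's judgement.** Section 7.10.2 names no assessor for CS; only the ECG section names the investigator. The split between classes 2 and 3 turns on abnormality.
- **That statistical power is lost.** No laboratory test is planned, and the remedy is descriptive, so power figures would describe neither.

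**Conclusion.** The point holds as a gap between sections. Section 5.1 names laboratory changes and 2.1 promises full safety information, but 7.10.2 describes no change from baseline, no baseline counterpart to the classes, and no full listing. The conclusion about shifts below the CS level comes from the text alone and needs no numerical assumption. It is limited to what the SAP describes, since the TFL shells may contain more.

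The size cannot be fixed from the documents. The 6% to 99% range for an empty value listing rests on normality, an assumed 0.75 SD shift, correlation 0.5 to 0.7, 1 to 20 samples and CS at 3 or 4 SD. It shows that the listing cannot be relied on to reveal a shift, not how often it would fail here. The change should be made, because the data are already held and the cost is small.

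**What to change.** In 7.10.2, add text to this effect:

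- All serum chemistry, hematology, urinalysis and CSF results will be listed by patient and visit, with normal ranges and CS/NCS flags.
- The three classes will be tabulated for each parameter against the patient's class at baseline, by regimen and overall.
- For quantitative parameters, observed values and change from baseline will be summarised by scheduled visit (n, mean, SD, median, minimum, maximum), by regimen and overall, descriptively and without tests.

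Amend 8.1 so that laboratory and CSF data are among the permitted summaries, and keep the listing of new CS profiles as a supplement. If the TFL shells already contain any of these outputs, say so in 7.10.2.

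The cost is SAP wording, some standard tables and listings for each laboratory panel, and a longer abbreviated report. No new data are needed: results and normal ranges are already collected and converted to SI units, and 7.1 already defines the summary format.

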7.10.3 ECG Evaluations

A listing of clinically significant ECG findings, as assessed by the investigator will be provided.

7.10.4 Vital Signs

The IT-administration vital signs will be presented in a listing.

7.10.5 Anti-rhHNS Antibody in Serum and CSF

Anti-rhHNS antibody status (ie, positive or negative) at each assessment time from baseline to the data cut-off date will be presented in listings based on serum and CSF samples.

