6.7.2 Physical Examination, Including Height, Weight, and Head Circumference

During the study, physical examinations will be performed at the time points indicated in the Schedules of Events. For Groups 1 and 2, full physical examinations will be conducted at Weeks 96, 120, 144, and 168, and for Groups 3A and 3B, full physical examinations will be conducted during the IDDD implantation period and at Weeks 24, 48, 72, 96, and 120. The remainder of physical examinations will be symptom-directed, including examinations during the safety follow-up period in patients who do not have the IDDD removed (partial or full device) at the end of the treatment period.

Physical examinations will include a review of the patient's general appearance, neurological examination, as well as evaluation of the body systems described in [Table 2](#), including the port and catheter track. Any abnormal change in findings will be recorded as an AE on the appropriate eCRF.

Table 2 Assessments for Physical Examinations

| Assessment | Assessment |
|-------------------------|-----------------|
| General appearance | Endocrine |
| Head and neck | Cardiovascular |
| Eyes | Abdomen |
| Ears | Genitourinary |
| Nose | Skin |
| Throat | Musculoskeletal |
| Chest and lungs | Neurological |
| Port and catheter track | |

Height and weight will be recorded for all patients.

The clinical site staff will be instructed to use calibrated scales for weight measurement where possible. The same scale is to be used at the clinical site for all patients at each specified time point during the study.

Head circumference will be measured for Groups 3A and 3B during the IDDD implantation period. All data will be recorded on the eCRF.

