6.7.5.2 Anti-rhHNS Antibodies and Biomarkers in CSF and Serum

An aliquot of each CSF sample collected will be quick frozen for subsequent analysis of anti-rhHNS antibody evaluation, exploratory proteomics biomarkers, and/or other CSF biomarkers.

Blood samples will be collected and evaluated at Shire or Shire-designated laboratories for the determination of serum anti-rhHNS antibodies.

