8. CHANGES IN THE CONDUCT OF THE STUDY OR PLANNED ANALYSES

8.1 Changes from the Analyses Planned in the Protocol

As this extension study will remain ongoing to allow for safety follow-up for patients with implanted devices (partial or full), despite the decision by Shire to terminate the development program, data for the treatment period of the study will be summarized in an abbreviated CSR. Not all data collected in this study will be analyzed. Summary statistics will only be presented for baseline characteristics, exposure of study drug, and adverse events. The data of selected efficacy endpoints will be presented in listings only. All outputs will be presented for safety population and no efficacy population will be defined. Information regarding the safety follow-up period will be analyzed after study completion and described in the final SAP.

The following data will not be analyzed: health status (ITQoL) and pharmacokinetic assessments.

However, SDTM data will be available for these endpoints.

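### Does the antibody listing leave out the enzyme-neutralizing results that section 5.1 counts as part of the primary safety assessment?

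*SAP*

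**What the plan says.** The document holds an earlier SAP, an interim SAP dated 26 May 2017 and an addendum for the safety follow-up period. The two SAPs treat antibodies almost identically; the references below are to the interim SAP unless stated.

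- **Section 5.1** makes safety the primary objective and lists seven ways of assessing it. The last is anti-rhHNS antibodies in CSF and serum, "including determination of antibodies having enzyme neutralizing activity".
- **Section 6.7.5.2** covers the samples. Aliquots of CSF are frozen for antibody work and, for serum, "Blood samples will be collected and evaluated at Shire or Shire-designated laboratories for the determination of serum anti-rhHNS antibodies". Neutralizing activity is not mentioned.
- **Section 7.10.5** gives the output: "Anti-rhHNS antibody status (ie, positive or negative) at each assessment time from baseline to the data cut-off date will be presented in listings", from serum and CSF samples.
- **Section 7.1** says of data other than pharmacokinetics and health economics: "The analysis methods for all other study data (demographic and baseline characteristics, efficacy variables, and safety variables) will be detailed in this SAP".
- **Section 8.1** carries the general statement "Not all data collected in this study will be analyzed". It restricts summary statistics to baseline characteristics, exposure and adverse events, and names only ITQoL and pharmacokinetics as not analyzed.
- **Section 10.1** refers the reader to the TFL shells for the list of outputs.

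**The concern.** A component named under the primary endpoint appears to go missing on the way to the outputs. Section 5.1 treats neutralizing activity as something to be determined in its own right. Section 7.10.5 then explains antibody status in brackets as positive or negative, and its wording reads as a definition rather than an example. A sample can hold antibodies that bind the enzyme without blocking it, so a positive status does not answer the question that section 5.1 raises.

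The silence also looks odd beside omissions the SAP does state. For KABC-II, section 7.8.2.1 says "these scores were considered invalid by the sites, hence no data for KABC-II will be presented"; for pharmacokinetics, section 7.9.1 says "hence no analysis on pharmacokinetic measurement and parameters will be provided". Section 2.1 promises complete safety reporting even though the study report is abbreviated. A reader holding only the listing as worded could not tell whether neutralizing activity was absent, not tested or not reported. If the results existed and were left out, part of the primary safety assessment would disappear without notice.

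**Working it through.** The SAP gives no sample size, power or error-rate calculation that bears on this point, so there is no figure to reproduce. The check is to follow the item through the text.

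**1. Where neutralizing activity appears.**

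| Place | Earlier SAP | Interim SAP |
|---|---|---|
| 5.1, safety assessment | named | named |
| 6.7.5.2, antibody samples | not mentioned | not mentioned |
| 7.10.5, antibody output | not mentioned | not mentioned |
| 8.1, data not analyzed | not named | not named |

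It is named in 2 of 2 versions of section 5.1, given an explicit output in 0 of 2 versions of section 7.10.5, and declared as dropped in 0 of 2 versions of section 8.1. The addendum's safety endpoints (section 4.2) contain no antibody item, so nothing later fills the gap. The textual observation is correct.

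**2. Does the text show that the results will be left out?** No. Section 10.1 places the list of outputs in the shells. The promise in section 7.1 concerns analysis methods, and a by-sample listing column needs none: there is no model, summary or derivation to specify. A neutralizing result can itself be recorded as positive or negative, so the bracket in section 7.10.5 does not exclude it, although it does not state it either.

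**3. Is this silence unusual in this SAP?** No. Other collected items have no stated output and are not named in section 8.1:

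- developmental delay scores are a secondary endpoint in section 5.2 but are not among the scores listed in section 7.8.2.1;
- the BSID-III social/emotional area appears in Table 1 but not among the subtests in section 7.8.2.1;
- liver and spleen volumes are measured under section 6.3.2 and have no output in section 7.

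For these the SAP relies on its general sentence, "Not all data collected in this study will be analyzed". The items dropped by name are therefore not a complete register, and absence from that group says little about neutralizing activity.

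**4. Are the other safety items in section 5.1 fully served?** Several are reported only in part. Section 7.10.3 lists only clinically significant ECG findings. Section 7.10.4 lists only the vital signs taken around IT administration. Physical examination has no output under section 7.10; it reaches the report through a recording rule in section 6.7.2, "Any abnormal change in findings will be recorded as an AE on the appropriate eCRF". Antibodies, reported as status by sample, are served in a similar way.

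**5. What would differ in the results?** Section 4.5 expects at most 21 patients. Antibody data are listed only, and the section 8.1 limit on summary statistics leaves no antibody table to alter. With a neutralizing column or without one, every status value, adverse event count and denominator stays the same.

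**The case for a change.** The strongest case for acting is that antibodies are reported only through this listing, so its content is the whole antibody report. How a result is displayed is SAP business rather than protocol business. Section 5.1 singles neutralizing activity out, and section 2.1 commits to complete safety reporting, which a general caveat in section 8.1 does not plainly override. The limit on summary statistics does not explain the silence either, since a listing is planned anyway. The remedy would be small: one extra column, or one sentence stating that the determination was not made.

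Much of this stands. Sections 5.1 and 7.10.5 do not match word for word, and a clause in either direction would have been tidier. What does not follow is that the plan goes wrong as it is. The listing rule yields no incorrect value, the output list sits in shells that may already carry the column, and the commitment in section 2.1 itself points the analyst towards showing whatever neutralizing results exist. A column limited to antibody-positive samples would also add an assumption of its own, because no section says which samples were tested for neutralizing activity or that testing depended on a positive screen.

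**Conclusion.** The concern is right about the wording and does not justify a change. Section 5.1 names a determination that section 7.10.5 does not repeat and section 8.1 does not declare dropped. That is missing detail in a listing description. A programmer working from sections 5.1 and 2.1 would place any available neutralizing result beside antibody status for the samples tested, and the study report would say so if none had been determined.

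The effect on estimates, tests, populations and summary tables is nil: antibody data are listed only, for at most 21 patients, in a study that section 2.1 says is not meant to contribute to the evaluation of effectiveness.

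This rests on two assumptions. The first is that the shells, which are not at hand, do not forbid showing neutralizing results. The second is that the section 2.1 commitment to full safety reporting is honored in the abbreviated report. If neutralizing results were held and deliberately withheld, that would be a failure of reporting, and nothing in this SAP shows it to be planned.
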